8.10.8. Unscheduled Visits

If the participant's parent(s)/legal guardian(s) reports redness or swelling at the injection site measuring >14 measuring device units (>7 cm), severe injection site pain, or a fever >40.0°C (>104.0°F) during the 7-day postvaccination period, a telephone contact must occur as soon as possible between the investigator or medically qualified designee and the participant's parent(s)/legal guardian(s) to assess if an unscheduled investigator site visit is required. Note that for a fever >40.0°C (>104.0°F), the participant's parent(s)/legal guardian(s) should be instructed not to delay seeking medical care, as appropriate, while arranging for an unscheduled visit if applicable. A visit should be scheduled as soon as possible to assess the extent of the injection site reaction, unless any of the following is true:

- The participant's parent(s)/legal guardian(s) is unable to bring the participant to the unscheduled visit.
- The reaction is no longer present at the time of the telephone contact.
- The participant's parent(s)/legal guardian(s) recorded an incorrect value in the e-diary (confirmation of an e-diary data entry error).

- The principal investigator (PI) or authorized designee determined it was not needed.

This telephone contact will be recorded in the participant's source documentation and the CRF.

If the participant's parent(s)/legal guardian(s) is unable to bring the participant to an unscheduled visit, or the PI or authorized designee determined it was not needed, any ongoing reactions must be assessed at the next study visit.

During the investigator site visit, the reactions should be assessed by the investigator or a medically qualified member of the study staff such as a study physician or a study nurse, as applicable to the investigator's local practice, who will:

- Measure rectal temperature (°C/°F).
- Measure minimum and maximum diameters of redness (if present).
- Measure minimum and maximum diameters of swelling (if present).
- Assess injection site pain in accordance with the grades provided in [Section 8.2.2](#) (if present).
- Assess for other findings associated with the reaction and record on the AE page of the CRF, if appropriate.

The investigator or an authorized designee will complete the unscheduled visit assessment page of the CRF.

The participant's parent(s)/legal guardian(s) will also be instructed to contact investigator site staff if the participant experiences any emergency room visit or hospitalization for decreased appetite, drowsiness/increased sleep, irritability, or local reaction within 7 days of vaccination.

The participant's parent(s)/legal guardian(s) will also be instructed to contact the investigator site to report any significant illness, medical event, or hospitalization that occurs during the study period. The investigator site should determine if an unscheduled visit to further evaluate the event is warranted in all such cases.

Additionally, study staff may contact the participant's parent(s)/legal guardian(s) to obtain additional information on Grade 3 events entered into the e-diary.

9. STATISTICAL CONSIDERATIONS

Methodology for summary and statistical analyses of the data collected in this study is described here and further detailed in a statistical analysis plan (SAP), which will be maintained by the sponsor. The SAP may modify what is outlined in the protocol where appropriate; however, any major modifications of the primary endpoint definitions or their analyses will also be reflected in a protocol amendment.

9.1. Estimands and Statistical Hypotheses

9.1.1. Estimands

The estimand corresponding to each primary, secondary, CCI objective is described in the table in Section 3. The estimands to evaluate the immunogenicity objectives for noninferiority are based on evaluable populations (Section 9.3). These estimands estimate the vaccine effect in the hypothetical setting where participants follow the study schedules and protocol requirements as directed. The estimand addresses the objective of estimating the maximum potential difference between 2 groups, since the impact of noncompliance is likely to diminish the observed difference between the 2 groups. Missing serology results will not be imputed. Immunogenicity results that are below the LLOQ will be set to $0.5 \times \text{LLOQ}$ in the analysis.

In the primary safety objective evaluations, missing e-diary data will not be imputed. Missing AE dates will be imputed according to Pfizer safety rules. No other missing information will be imputed in the safety analysis.

9.1.2. Statistical Hypotheses

9.1.2.1. Pneumococcal Immunogenicity Hypotheses

9.1.2.1.1. Percentage of Participants With Predefined Pneumococcal Serotype-Specific IgG Concentration 1 Month After Dose 3 (Primary Pneumococcal Immunogenicity Objectives)

Hypothesis testing will be used to assess the noninferiority of 20vPnC to 13vPnC for percentages of participants with predefined pneumococcal serotype-specific IgG concentrations 1 month after Dose 3. The null hypothesis (H_{0A}) for a serotype is

$$H_{0A}: \pi_{20vPnC} - \pi_{13vPnC} \leq -10\%,$$

with a 10% margin for noninferiority, where

- π_{20vPnC} is the percentage of participants achieving an IgG antibody concentration of predefined level in the 20vPnC group for the serotype 1 month after Dose 3;
- If the serotype is from the 13 matched serotypes (1, 3, 4, 5, 6A, 6B, 7F, 9V, 14, 18C, 19A, 19F, 23F) in 13vPnC, π_{13vPnC} is the percentage of participants achieving a predefined IgG concentration level for the serotype from the 13vPnC group 1 month after Dose 3;

- If the serotype is from the 7 additional serotypes (8, 10A, 11A, 12F, 15B, 22F, 33F) in 20vPnC, π_{13vPnC} is the percentage of participants achieving a predefined IgG concentration level from the serotype with the lowest percentage 1 month after Dose 3 among the 13 serotypes from the 13vPnC group, provided that the lowest percentage is not from serotype 3. If the lowest percentage in the 13vPnC group is from serotype 3, the next lowest percentage in the 13vPnC group will be used in the comparison. Historical data suggest that serotype 3 behaves somewhat differently from the other serotypes in 13vPnC; therefore, IgG results from serotype 3 will not be used in the comparison to assess the noninferiority of the 7 additional serotypes.
- The predefined levels for serotype-specific IgG concentrations are 0.35 $\mu\text{g/mL}$ for all serotypes in 20vPnC except that the predefined levels are 0.23 $\mu\text{g/mL}$, 0.10 $\mu\text{g/mL}$, and 0.12 $\mu\text{g/mL}$ for serotypes 5, 6B, and 19A, respectively.

The null hypothesis (H_{0A}) will be rejected and noninferiority of 20vPnC to 13vPnC for the percentage of participants with predefined IgG concentration level will be declared for a serotype if the lower bound of the 2-sided 95% CI for the difference (20vPnC – 13vPnC) in percentages, based on the Miettinen and Nurminen method, is greater than –10% (10% noninferiority margin).

9.1.2.1.2. Pneumococcal Serotype-Specific IgG GMCs 1 Month After Dose 4 (Primary Pneumococcal Immunogenicity Objectives)

Hypothesis testing will be used to assess noninferiority of 20vPnC to 13vPnC for pneumococcal serotype-specific IgG GMCs 1 month after Dose 4. The null hypothesis (H_{0B}) for a serotype is

$$H_{0B}: \ln(\mu_{20vPnC}) - \ln(\mu_{13vPnC}) \leq \ln(0.5)$$

where $\ln(0.5)$ corresponds to a 2-fold margin for noninferiority and

- $\ln(\mu_{20vPnC})$ is the natural log of the geometric mean IgG concentration in the 20vPnC group for that serotype 1 month after Dose 4;
- If the serotype is from the 13 matched serotypes (1, 3, 4, 5, 6A, 6B, 7F, 9V, 14, 18C, 19A, 19F, 23F), $\ln(\mu_{13vPnC})$ is the natural log of the geometric mean IgG concentration in the 13vPnC group 1 month after Dose 4;
- If the serotype is from the 7 additional serotypes (8, 10A, 11A, 12F, 15B, 22F, 33F) in 20vPnC, $\ln(\mu_{13vPnC})$ is the natural log of the geometric mean IgG concentration for the serotype with the lowest IgG GMC 1 month after Dose 4 among the 13 serotypes from the 13vPnC group, provided that the lowest GMC is not from serotype 3. If the lowest GMC in the 13vPnC group is from serotype 3, the next lowest GMC in the 13vPnC group will be used in the comparison. As stated in [Section 9.1.2.1.1](#), historical data suggest that serotype 3 behaves somewhat differently from the other serotypes in 13vPnC; therefore,

IgG results from serotype 3 will not be used in the comparison to assess the noninferiority of the 7 additional serotypes.

The null hypothesis (H_{0B}) will be rejected and noninferiority of 20vPnC to 13vPnC for the pneumococcal serotype-specific IgG GMC will be declared for a serotype if the lower bound of the 2-sided 95% CI for the IgG GMR of 20vPnC to 13vPnC is greater than 0.5 (2-fold noninferiority margin).

9.1.2.1.3. Pneumococcal Serotype-Specific IgG GMCs 1 Month After Dose 3 (Key Secondary Pneumococcal Immunogenicity Objectives)

Hypothesis testing to assess noninferiority of 20vPnC to 13vPnC for pneumococcal serotype-specific IgG GMCs 1 month after Dose 3 will be performed similarly to that for IgG GMCs 1 month after Dose 4, as described in [Section 9.1.2.1.2](#), with $\ln(\mu_{20vPnC})$ and $\ln(\mu_{13vPnC})$ being the natural log of the geometric mean IgG concentrations 1 month after Dose 3 from the 20vPnC and 13vPnC groups, respectively. If the serotype is from the 7 additional serotypes (8, 10A, 11A, 12F, 15B, 22F, 33F) in 20vPnC, $\ln(\mu_{13vPnC})$ is the natural log of the geometric mean IgG concentration for the serotype with the lowest IgG GMC among the 13 serotypes from the 13vPnC group, provided that the lowest GMC is not from serotype 3. If the lowest GMC in the 13vPnC group is from serotype 3, the next lowest GMC in the 13vPnC group will be used in the hypothesis testing.

The null hypothesis H_{0B} will be rejected and noninferiority of 20vPnC to 13vPnC for the pneumococcal serotype-specific IgG GMC will be declared for a serotype if the lower bound of the 2-sided 95% CI for the IgG GMR of 20vPnC to 13vPnC for the serotype is greater than 0.5 (2-fold noninferiority margin).

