9.1.3. Multiplicity Considerations

Pneumococcal Immunogenicity Evaluation

For the primary pneumococcal immunogenicity objectives comparing percentages of participants with predefined serotype-specific IgG concentration levels 1 month after Dose 3, noninferiority will be assessed by the hypothesis test as described in [Section 9.1.2.1.1](#) at an alpha level of 0.05 for each serotype. The primary pneumococcal immunogenicity objectives will be achieved if the noninferiority of 20vPnC to 13vPnC for the percentage of participants with the predefined IgG concentration level at 1 month after Dose 3 is established for all 20 serotypes.

For the primary pneumococcal immunogenicity objectives comparing serotype-specific IgG GMCs 1 month after Dose 4, noninferiority will be assessed by the hypothesis test as described in [Section 9.1.2.1.2](#) at an alpha level of 0.05 for each serotype. The primary pneumococcal immunogenicity objectives will be achieved if the noninferiority of the IgG GMCs from the 20vPnC group compared to the 13vPnC group at 1 month after Dose 4 is established for all 20 serotypes.

The overall primary pneumococcal immunogenicity objectives will be achieved if noninferiority of 20vPnC comparing to 13vPnC based on both the percentage of participants with predefined serotype-specific IgG concentration levels at 1 month after Dose 3 and the serotype-specific IgG GMC at 1 month after Dose 4 is demonstrated for all 20 serotypes. Therefore, the overall type I error rate for the primary immunogenicity assessment of the pneumococcal immune response of 20vPnC is well controlled at the 0.05 level.

Concomitant Immunogenicity Evaluation

For the primary concomitant immunogenicity objective comparing immune responses induced by concomitant vaccine antigens at 1 month after Dose 3 from the 20vPnC group to that from the 13vPnC group, noninferiority is assessed by a hypothesis test (Section 9.1.2.2.1) at an alpha level of 0.05 for each concomitant vaccine antigen. The primary concomitant immunogenicity objective will be met if noninferiority is achieved for all concomitant vaccine antigens, diphtheria toxoid, tetanus toxoid, pertussis antigens (PT, FHA, PRN), HBsAg, poliovirus strains, and Hib. Therefore, the type I error rate for the concomitant immunogenicity assessment is well controlled at the 0.05 level.

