9.2. Sample Size Determination

9.2.1. Sample Size Consideration for Primary Pneumococcal Immunogenicity Objectives

A total of approximately 2000 enrolled participants will yield approximately 1600 evaluable participants assuming a 20% nonevaluable rate for the study, resulting in approximately 800 evaluable participants for each vaccine group with a 1:1 randomization ratio between the 20vPnC and 13vPnC groups. Sample size and power for the primary pneumococcal immunogenicity objectives associated with IgG concentration results at 1 month after Dose 3 and 1 month after Dose 4 are assessed based on simulations with assumptions supported by IgG results from an internal Pfizer Phase 2 infant study of 20vPnC (B7471003) following multivariate log-normal distributions **CCI**

Assuming the true GMCs and variance-covariance matrices for the 20 serotype-specific IgG concentrations from both 20vPnC and 13vPnC groups are the same as those observed from Study B7471003, with 800 evaluable participants from each vaccine group, the study has approximately 93% probability to show at least 37 (out of 40 total) positive noninferiority assessments comparing IgG results between the 20vPnC and 13vPnC groups, based on percentages of participants with predefined serotype specific IgG concentration levels at 1 month after Dose 3 and serotype-specific IgG GMCs 1 month after Dose 4 for the 20 serotypes.

CCI [Redacted]

[Redacted]	[Redacted]	[Redacted]
[Redacted]	[Redacted]	[Redacted]
[Redacted]	[Redacted]	[Redacted]

CCI [Redacted]

CCI [Redacted]

CCI [Redacted]

CCI [Redacted]

CCI

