## 5.1. Hypotheses and Decision Rules

### 5.1.1. Pneumococcal Immunogenicity Hypotheses

#### 5.1.1.1. Percentage of Participants With Predefined Pneumococcal Serotype-Specific IgG Concentration 1 Month After Dose 3 (Primary Pneumococcal Immunogenicity Objectives)

Hypothesis testing will be used to assess the NI of 20vPnC to 13vPnC for percentages of participants with predefined pneumococcal serotype-specific IgG concentrations 1 month after Dose 3 (see [Section 3.1.2](#) for predefined concentrations). The null hypothesis ( $H_{0A}$ ) for a serotype is

$$H_{0A}: \pi_{20vPnC} - \pi_{13vPnC} \leq -10\%,$$

with a 10% margin for NI, where

- $\pi_{20vPnC}$  is the percentage of participants achieving the IgG concentration of predefined level in the 20vPnC group for the serotype 1 month after Dose 3;
- If the serotype is from the 13 matched serotypes (1, 3, 4, 5, 6A, 6B, 7F, 9V, 14, 18C, 19A, 19F, 23F) in 13vPnC,  $\pi_{13vPnC}$  is the percentage of participants achieving the predefined IgG concentration level for the serotype from the 13vPnC group 1 month after Dose 3;
- If the serotype is from the 7 additional serotypes (8, 10A, 11A, 12F, 15B, 22F, 33F) in 20vPnC,  $\pi_{13vPnC}$  is the percentage of participants achieving a predefined IgG concentration level from the serotype with the lowest percentage 1 month after Dose 3 among the 13 serotypes from the 13vPnC group, provided that the lowest percentage is not from serotype 3. If the lowest percentage in the 13vPnC group is from serotype 3, the next lowest percentage in the 13vPnC group will be used in the comparison. Historical data suggest that serotype 3 behaves somewhat differently from the other serotypes in 13vPnC; therefore, IgG results from serotype 3 will not be used in the comparison to assess the NI of the 7 additional serotypes.

The null hypothesis ( $H_{0A}$ ) will be rejected and NI of 20vPnC to 13vPnC for the percentage of participants with predefined IgG concentration level will be declared for a serotype if the lower bound of the 2-sided 95% CI for the difference (20vPnC – 13vPnC) in percentages, based on the Miettinen and Nurminen method, is greater than –10% (10% NI margin).

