#### **5.2.2.2. Geometric Mean Ratios**

Where appropriate, GMRs and their 2-sided 95% CIs will be derived by calculating differences in means and CIs on the natural log scale of the assay results based on the t-distribution (allowing for unequal variances), and then exponentiating the results. The difference in means, on the natural log scale, will be the 20vPnC group minus the 13vPnC group.

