#### 6.1.2.1.2. Supplementary Analysis

As a supplemental analysis to the main analysis that assesses NI, for each of the 7 additional serotypes, the percentage difference (and its 2-sided 95% CI) between the 2 groups (20vPnC – 13vPnC), with the comparator being the percentage of participants achieving predefined IgG concentrations for that corresponding serotype from the 13vPnC group, will be provided.

As a supportive analysis to the main analysis, an additional summary may be provided using an alternative reference concentration of 0.15 µg/mL for all serotypes.

#### 6.1.2.2. Pneumococcal Serotype-Specific IgG Concentrations 1 Month After Dose 4

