**6.1.2.2.2. Supplementary Analysis**

As a supplementary analysis to support the interpretation of the main analysis, for each of the 7 additional serotypes, the GMR (and its 2-sided 95% CI) of 20vPnC to 13vPnC at 1 month after Dose 4, with the comparator being the IgG GMC of the corresponding serotype in the 13vPnC group, will be calculated.

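### Protocol 9.1.3 claims type I error control without condition, but the 7 additional serotypes are tested against the observed-lowest of 12 13vPnC serotypes with an unadjusted interval

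*Protocol*

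**What the plan says.** Protocol 9.1.2.1.1 compares each of the 7 additional serotypes with the 13vPnC percentage "from the serotype with the lowest percentage 1 month after Dose 3 among the 13 serotypes from the 13vPnC group". Section 9.1.2.1.2 does the same for GMCs, with "the serotype with the lowest IgG GMC 1 month after Dose 4 among the 13 serotypes from the 13vPnC group". If serotype 3 is lowest, the next lowest is used, which leaves 12 candidates. No comparator is named in advance, and the analysis table in 9.4.1 takes whichever result is lowest in the trial's own 13vPnC data.

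Noninferiority is declared when the lower limit of a 2-sided 95% interval clears the margin (-10 percentage points, or a ratio of 0.5). The interval is Miettinen-Nurminen for percentages. For ratios the SAP uses the "t-distribution (allowing for unequal variances), and then exponentiating the results".

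Section 9.1.3 tests each serotype at 0.05, requires success for all 20 serotypes on both endpoints, and concludes that the "overall type I error rate for the primary immunogenicity assessment of the pneumococcal immune response of 20vPnC is well controlled at the 0.05 level".

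SAP 5.1.1.1 and 5.1.1.2 repeat the rule, including that "IgG results from serotype 3 will not be used in the comparison to assess the NI of the 7 additional serotypes". The supplementary analyses for these serotypes use a different comparator: in SAP 6.1.2.1.2, "with the comparator being the percentage of participants achieving predefined IgG concentrations for that corresponding serotype from the 13vPnC group"; in SAP 6.1.2.2.2, "with the comparator being the IgG GMC of the corresponding serotype in the 13vPnC group".

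**The concern.** Requiring every test to pass controls the overall error only if each component test holds its own level. It covers the multiplicity of 20 serotypes and two time points. It does not cover a comparator picked from 12 by looking at the data and then treated as if it had been fixed beforehand.

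An observed minimum tends to fall below the true minimum, and that shift favours 20vPnC. The supplementary analyses do not help: comparing with the same serotype in the 13vPnC arm, which does not contain it, answers another question.

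What is at stake is the error statement of the pivotal immunogenicity comparison, for 14 of its 40 tests (7 serotypes at 2 time points). The 13 matched serotypes have fixed comparators and are unaffected.

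**Working it through.** **Inputs from the documents.** About 800 evaluable per group (Protocol 9.2.1); margins of -10 points and 0.5; lower limit of a 2-sided 95% interval, so nominally 2.5% in the tested tail; 12 candidate comparators; all 40 tests must pass.

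**Assumptions, because the documents print no values.** Lowest 13vPnC rate 80-90%; ln SD 1.0; correlation between serotypes 0 to 0.7, with 0.9 as a check; similar standard errors unless stated.

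**1. The plan's own figure.** If all tests must pass, the overall error is at most the largest single-test error, here 0.05 two-sided or 0.025 in the tested tail. Exact enumeration of the Miettinen-Nurminen rule at n = 800 with one fixed comparator gives 2.4-2.5%. The argument is sound when the comparator is fixed.

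**2. What selection does.** The null for an additional serotype is π20 ≤ min(π13) - 10, so it is true only if the serotype is at or beyond the margin against all 12 comparators. With similar standard errors, passing against the observed lowest amounts to passing any one of 12 unadjusted tests. The crude bound is 12 × 0.025 = 0.30.

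**3. Normal-theory error.** One additional serotype is exactly at the margin and the others pass easily. With T and C_j the standardised estimates,

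error = P{(T - min C_j)/√2 > 1.96}.

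| Comparators tied for lowest | Correlation 0.7 to 0 | Correlation 0.9 |
|---|---|---|
| 1 | 2.5% | 2.5% |
| 2 | 3.7-4.6% | 3.2% |
| 3 | 4.6-6.3% | 3.7% |
| 4 | 5.2-7.8% | 4.0% |
| 12 (extreme) | 8.1-16.0% | 5.2% |

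The printed 0.05 is passed from 3 exact ties at correlation up to 0.5, or from 4 ties at 0.7.

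**4. With gaps (correlation 0.7 to 0).**
- Three comparators, the other two higher by 0.25 SE: 3.7-4.9%; by 0.5 SE: 3.1-4.0%; by 1 SE: 2.7-3.1%.
- Lowest 1 SE below 11 tied others: 2.9-4.9%; 2 SE below: 2.5-2.7%.

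At 85%, 1 SE = √(0.85 × 0.15/800) = 1.26 points, so 0.25 SE is 0.3 points and 2 SE is 2.5 points. At ln SD 1.0, 1 SE = 1/√800 = 0.035, so 0.25 SE is 0.9% and 2 SE is 7% of a GMC.

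**5. Exact Miettinen-Nurminen error, independent comparators.**

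| Lowest rate | 1 | 2 tied | 3 tied | 4 tied | 12 tied |
|---|---|---|---|---|---|
| 80% | 2.5% | 4.4% | 6.0% | 7.4% | 14.3% |
| 85% | 2.5% | 4.3% | 5.9% | 7.1% | 13.6% |
| 90% | 2.5% | 4.3% | 5.6% | 6.8% | 12.6% |

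At 85%, if the other 11 are 1, 2 or 3 points higher, the error is 5.7%, 3.1% or 2.6%.

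**6. Two additional serotypes at the margin at the same time point.** The all-must-pass rule then brings the error to 0.9-2.0% (2 tied), 1.3-2.5% (3 tied) or 4.4-5.0% (12 tied). The exposure is therefore a single borderline serotype.

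**The case against.** The strongest reply is that the printed claim is 0.05 while the decision rule spends only 0.025, so there is a factor of two in hand. Two ties, or three comparators with small gaps, stay below 5%. An excess needs several near-tied minima, one serotype exactly at the margin and everything else passing easily. Twelve comparators evenly spaced 0.5 SE apart give only 2.9-3.6%; at 0.25 SE apart they give 3.5-5.2%. All serotypes are measured in the same infants, so zero correlation is pessimistic. Redactions in the synopsis, in 9.2.1, in 9.4.1 and after the SAP's general methods may hide relevant text.

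Much of this stands, and it limits the finding to a conditional one. It does not rescue the sentence. Section 9.1.3 states no condition, and three or four near-ties can pass 0.05. Correlation helps less for percentages than it seems: a latent correlation of 0.9 between concentrations becomes about 0.65-0.69 between responder indicators, and the error with 12 ties is then still 7.0-7.4%. The readable part of 9.2.1 simulates power, not type I error. Hidden text elsewhere cannot change the reason that 9.1.3 itself gives, which is readable in full.

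**Conclusion.** The concern holds. The unconditional statement in 9.1.3 is not supported for the 14 tests of the additional serotypes. Their worst-case error exceeds the nominal 2.5% as soon as two comparators are close to tied for lowest. It exceeds the printed 0.05 from three or four ties, depending on correlation. The control is essentially restored when one 13vPnC serotype is lowest by about 2 SE.

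This is missing support for a claim, not evidence that this trial's error is above 0.05: which case applies depends on 13vPnC spacings and correlations that the documents do not print. The sizes rest on 800 per group, similar standard errors and the assumed rates, SD and correlations above. The point should be fixed, but it does not call for a new primary criterion.

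**What to change.** Keep the primary rule and the observed-lowest comparator.

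1. **Restate Protocol 9.1.3, and put the same sentence in SAP 5.1**, where no error-control text is visible. Say that the level of these 14 tests is claimed only when one 13vPnC serotype is clearly lowest, by about 2 SE. The alternative is more informative: print the attainable error from the Phase 2 (B7471003) GMCs and the "variance-covariance matrices for the 20 serotype-specific IgG concentrations from both 20vPnC and 13vPnC groups" that 9.2.1 already uses.

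2. **Before unblinding, add a sensitivity lower bound to SAP 6.1.2.1.2 and 6.1.2.2.2.** Simulate the 12 comparators as tied, with the covariance estimated in the 13vPnC arm, and the additional serotype with its own standard error. Replace 1.96 by the 97.5% quantile of the studentised difference from the minimum. Do not fix one value: it runs from 2.39 (SE ratio of additional to comparator 1.5, correlation 0.7) to 2.85 (ratio 0.5, correlation 0). With independent comparators, a fixed 2.77 would give 2.7-3.1% at ratios 0.8 to 0.5.

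**Cost.** One paragraph, two SAP insertions and a short simulation. The primary criterion and the stated 93% probability of at least 37 of 40 successes do not change. By contrast, a Bonferroni correction over 12 in the primary test would cut one serotype's power from 99.2% to 93.0% at a true difference of -2 points, and from 89% to 62% at -4 (lowest rate 85%, clearly separated).

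A borderline serotype could pass the primary rule and miss the sensitivity bound. For 75% against 85%, the SE of the difference is √[(0.85 × 0.15 + 0.75 × 0.25)/800] = 1.98 points. The bound then sits lower by (2.45 - 1.96) × 1.98 = 1.0 to (2.72 - 1.96) × 1.98 = 1.5 points. For a GMR with ln SD 1.0, the SE is √(2/800) = 0.05, and the bound is lower by 1 - exp(-0.53 × 0.05) = 2.6% to 1 - exp(-0.81 × 0.05) = 4.0% (critical values 2.49 and 2.77).
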